9.2 Medical Conditions

1. During the follow up phone visits, the subject will be asked for any adverse event or medication change since the medical history/diary at baseline.
2. Investigators will determine if any adverse event should be further studied. All actions will be recorded with medical condition and dates of adverse event and medication taken. The donor will be contacted and tested, if necessary.
3. Subjects should be instructed on treatment days to contact the study personnel if they have any questions regarding an adverse event or the appropriateness of a medication after FMT.

9.3 Monitoring for Safety

The following definitions of terms are guided by the International Conference of Harmonization and US Code of Federal Regulations (21 CFR 312.32).

9.3.1 Severity

The adverse event will be documented according to the following descriptors:

- *Mild*: associated with no limitation of usual activities or only slight discomfort
- *Moderate*: associated with limitation of usual activities or significant discomfort
- *Severe*: associated with inability to carry out usual activities or very marked discomfort

9.3.2 Relationship

The relationship of an adverse event to FMT will be assigned by the Investigator according to the following definitions:

- *Probable*: a reaction that follows a reasonable temporal sequence from the procedure that follows a known or expected response pattern to the suspected procedure and that could not be reasonably explained by the known characteristics of that subject's clinical state
- *Possible*: a reaction that follows a reasonable temporal sequence from the procedure that follows a known or expected response pattern to the procedure but could readily have been produced by a number of other factors

- *Unlikely*: a reaction that does not follow a reasonable temporal sequence from the procedure but for which causality from FMT cannot be ruled out.
- *Not related*: a reaction for which sufficient data exist to indicate that the etiology is unrelated to the procedure

9.4 Pre-existing Signs and Symptoms and Medical Conditions

Medical conditions that are present at or before the procedure that manifest with the same severity or frequency will not be recorded as an adverse event. Similarly, signs or symptoms related to a pre-existing disease will not be recorded as adverse event unless there is an increase in the severity or frequency of the signs or symptoms. The pre-existing conditions will be recorded in the Medical History.

9.5 Progression of Underlying Conditions and Anticipated events as an Adverse Event

If the symptoms of the primary CDI continue on the study, this is not an AE. If new symptoms develop or worsen after treatment, this is considered an AE.

Anticipated events include diarrhea, nausea, vomiting, gas/flatulence, abdominal distension, abdominal cramps/pain, constipation, rectal bleeding, fatigue/malaise, chills/shivering and fever (> 99.9 F), and may or may not be causally related to the FMT treatment or CDI. These anticipated events will be solicited from subjects at enrollment visit, via pre-treatment diary and at follow-up phone visits. For blinded treatment groups (1-3), mild to moderate diarrhea resulting from taking bowel prep starting a day before treatment and/or mild constipation from taking Imodium on treatment day up to one day after treatment are expected side effects, and should not be recorded as adverse events.

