DEFINITION OF TREATMENT FAILURE	Treatment failure is defined as the presence of diarrhea (passage of ≥ 3 watery stools per 24-hour period for two consecutive days) and C. difficile toxin A/B positive stool within 60 days of FMT treatment plus receipt of anti- C. difficile antibiotics.
STUDY AGENT, DOSE OF ADMINISTRATION	
Processed intestinal bacteria from a screened healthy donor will be administered lyophilized FMT to be given by the oral route. FMT will be given as follows:
 
 1. Group 1: With bowel prep and Imodium 1st treatment day, lyophilized product generated from 50g of stool 2nd treatment day, lyophilized product generated from 50g of stool 2. Group 2: With bowel prep and Imodium 1st treatment day, lyophilized product generated from 100g of stool 2nd treatment day, lyophilized product generated from 50g of stool 3. Group 3: With bowel prep and Imodium 1st treatment day, lyophilized product generated from 100g of stool 2nd treatment day, lyophilized product generated from 100g of stool 4. Unblinded Group 4: (Without bowel prep and Imodium) 1st treatment day, lyophilized product generated from 100g of stool 2nd treatment day, lyophilized product generated from 100g of stool
EFFICACY EVALUATION	
Primary Endpoint:
 
 • Safety of FMT (lyophilized capsules with various doses) • Prevention of subsequent bouts of CDI in 60 days post FMT. • Safety of FMT (lyophilized capsules with same doses) without using pre-FMT bowel preparation and Imodium • Prevention of subsequent bouts of CDI in 60 days post FMT without using pre-FMT bowel preparation and Imodium. 
Secondary Endpoint:
 
 • To characterize improvement in microbiota diversity from baseline in subjects treated with various doses of lyophilized capsules.

SAFETY EVALUATION	To ensure safe study conduct during the study, an independent, non-blinded, external Data and Safety Monitoring Board (DSMB) will be established to perform safety evaluations on an ongoing basis. A DSMB charter will be developed and will detail the review of the safety data. The DSMB will have the power to stop the trial.
STUDY STOPPING RULES	Study may be halted or discontinued if the DSMB identifies a trend of more illnesses or side effects in one or more of the treatment groups.

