5.3 Method of Assigning Subjects to Study and Treatment

The four groups will be assigned randomly on 1:1:1:1 ratio by computer table randomization method at the University of Texas School of Public Health. After enrollment of subject in the study, the study coordinator will send an email to the authorized person for randomization at the University of Texas School of Public Health including the schedule (date and time) of study procedure. The study coordinator will receive an email from the authorized person providing the subject identification number and confirmation of date and time for study drug delivery. For subjects randomized to unblinded treatment group 4, it will be noted in the email not to use bowel prep and Imodium.

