- Assess subject for solicited symptoms such as diarrhea (passage of ≥ 3 watery stools per 24-hour period for two consecutive days), nausea, vomiting, gas/flatulence, abdominal distension, abdominal cramps/pain, constipation, rectal bleeding, fatigue/malaise, chills/shivering and fever (>99.9 F) for up to 60 days after treatment.
- If CDI recurrence is suspected, subjects should be recommended to contact their physician to perform a stool test for *C. difficile*. EPDL will test scheduled stool specimens and any unscheduled illness stool submitted up to days 60-70 after treatment for *C. difficile* toxins A/B in weekly batches but this should not delay treatment. If the test is positive, they should be treated by their physician. The Principal Investigator will be available for consultation with the attending physician. A form letter may be faxed or emailed to subject's physician about CDI recurrence.
- Subject will be reminded to submit completed diary (except on follow up visit Day 1) and stool sample (except on follow up visit Day 180) and to put stool collection date on provided container (if already submitted, stool collection date should be confirmed).
- Stool samples will be collected at home by the subject and dropped off at the EPDL in the University of Texas School of Public Health in transportation provided containers with ice pack within 6 hours of collection if possible or as quickly as possible (excluding weekends and holidays). Stool sample will not be collected for follow up visit Day 180. If the subject is unable to bring stool sample for any reason (e.g. out of town), subject will be asked to ship the sample by Federal Express as expeditiously as possible. A FedEx shipping label, ice pack, Styrofoam container with shipping box and instructions will be provided to the subject to ship stool sample if they are not able to hand deliver to the EPDL. The EPDL will be closed on weekends and holidays. If the follow-up day falls on Friday, Saturday or Sunday, subjects can ship the sample on Thursday or the following Monday. Stool samples that are received out of window are not a protocol deviation; however, missed stool samples are a protocol deviation.

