9.6 Recording and Documenting Adverse Event

The study team must completely and promptly record each new adverse event and serious adverse event that occurs after the procedure, even if the relationship of adverse event to the procedure is assessed by the Investigator to be “unlikely” or “not related”. In addition, the investigator must document and follow serious adverse events and adverse events of special interest that occur from the procedure through 180-200 days after the FMT. The Investigator should attempt, if possible, to establish a diagnosis based on the presenting signs and symptoms. If an adverse event meets the definition of a serious, unexpected and suspected (related to study drug/procedure) adverse reaction (SUSAR) then the Investigator must also complete the serious adverse event form/IND safety report, and send any supporting source documents to the University of

Texas Health Science Center IRB and FDA as soon as the event is discovered within the defined timeline.

At each visit, after the subject has had an opportunity to mention any problems spontaneously, the Investigator (or designee) will inquire about adverse event by asking the standard questions listed, such as:

- Have you had any new medical problems since your last visit?
- Have any medical problems present at your last visit changed, i.e., stopped, worsened, or improved?
- Have you taken any new medicines, other than study drug, since your last visit?

Any spontaneous adverse event information provided by the subject will be recorded. If an adverse event has not resolved at the time of the final visit, the Investigator should evaluate the status of the adverse event at the follow-up phone contact and reflect the status of the adverse event (e.g. ongoing or resolved).

The DSMB will issue a final report identifying adverse events related to study drug.

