10.2.3 Analysis Populations

Two primary analyses will be performed:

- 1) Analysis for safety and efficacy between three groups (1-3) receiving varied doses of lyophilized product generated from stool (50g for both treatment days; 100g on the first treatment day and 50g on the second treatment; 100g for both treatment days)
- 2) Analysis for safety and efficacy between two groups (3 and 4) with and without bowel preparation and Imodium receiving same high doses of lyophilized product (100g for both treatment days).

- All analyses will be conducted using the intent-to-treat population. Intent-to-treat is defined as all subjects who have started the procedure.
- Listings and summary tables with descriptive statistics will be prepared for demographic data (gender, date of birth, race/ethnicity), and medical history data.

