10.2.5 Analyses of Safety

All adverse events and serious adverse events will be coded using the Medical Dictionary for Regulatory Activities Version 12.0, which is a registered trademark of the International Federation of Pharmaceutical Manufacturers and Associations. The number and percentage of subjects reporting at least one occurrence of an adverse event and/or serious adverse event for each system organ class and preferred term will be tabulated. Term will also be tabulated by severity and by the relationship to the procedure. For multiple occurrences of the same adverse event with different severities, the adverse event with the highest severity will be tabulated. For multiple occurrences of the same adverse event with different relationships to the procedure (related and not related); the adverse event will be tabulated as related. All adverse events and or serious adverse events for all subjects will be presented in data listings. Narratives will also be prepared for each serious adverse event.

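### Early low-grade diarrhea and constipation are recorded under different rules in groups 3 and 4, so the primary safety comparison of these groups can undercount them in group 3 only

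*Combined protocol and SAP*

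**What the plan says.** Section 9.5 lists diarrhea and constipation among the anticipated events solicited from all subjects, then makes an exception for some groups: "For blinded treatment groups (1-3), mild to moderate diarrhea resulting from taking bowel prep starting a day before treatment", and mild constipation from Imodium between treatment day and one day after, "are expected side effects, and should not be recorded as adverse events". The sentence can be read so that the one-day limit covers only constipation or covers diarrhea too. Both exclusions depend on cause.

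Nothing equivalent applies to group 4, which takes neither prep nor Imodium. There the general rule in 9.6 governs: each new post-procedure event is recorded, "even if the relationship of adverse event to the procedure is assessed by the Investigator to be" unlikely or not related.

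Section 10.2.3 names two primary analyses. The second is "Analysis for safety and efficacy between two groups (3 and 4) with and without bowel preparation and Imodium", both on the same 100 g per day. The synopsis lists as a primary endpoint "Safety of FMT (lyophilized capsules with same doses) without using pre-FMT bowel preparation and Imodium". Section 10.2.5 describes the output: the "number and percentage of subjects reporting at least one occurrence of an adverse event and/or serious adverse event", by system organ class and preferred term.

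Group 4 is openly unblinded. Section 5.3 says of the randomization email to the coordinator: "For subjects randomized to unblinded treatment group 4, it will be noted in the email not to use bowel prep and Imodium". Sections 7.2 and 8.3.1 have staff check prep and Imodium in groups 1-3 on Day 1.

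**The concern.** Prep and Imodium are the only planned difference between groups 3 and 4. The recording rule differs between these two groups for the symptoms that prep and Imodium are expected to cause. An event that is never recorded as an AE cannot enter the table in 10.2.5.

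Two consequences follow, and they should be kept apart.

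- **Omission.** Even if every cause is judged correctly, low-grade prep or Imodium effects after dosing are absent from group 3's counts. A tolerability gain from leaving prep out could not show for those events.
- **Misattribution.** An early low-grade event in group 3 that the product caused, but that is put down to prep or Imodium, is dropped. The same event in group 4 is recorded. Section 9.5 does not say who decides the cause. The study team records AEs, it knows who took prep, and no blinded adjudication is described.

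Both act in one direction: group 3's recorded counts can fall and group 4's cannot. The table could understate the cost of prep and Imodium, or make omitting them look worse than it is.

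**Working it through.** The plan gives no AE rate and no safety power, so there is no figure of its own to reproduce. The rules come first, then an illustration on stated assumptions.

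**Rules side by side, from dosing onward**

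| Event | Group 3 | Group 4 |
|---|---|---|
| Mild or moderate diarrhea, attributed to prep | Not recorded (9.5) | Cannot arise; any new early diarrhea is recorded (9.6) |
| Mild constipation to one day after, attributed to Imodium | Not recorded (9.5) | Cannot arise; any new early constipation is recorded (9.6) |
| Same symptoms, attributed to the product or another cause | Recorded | Recorded |
| Severe diarrhea; moderate or later constipation; serious AEs | Recorded | Recorded |

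Moderate diarrhea in Table 2 is an increase of 4 to 6 stools over baseline in 24 hours, so the exclusion reaches beyond trivial events.

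**Illustration of misattribution**

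Input from the plan: 90 per group (10.2.2). Assumptions: the same true rate in both groups, 10% or 20% (9 or 18 of 90); the share of affected subjects whose only recordable event of that type is early and low-grade, 50% or 100%; half of those misattributed in group 3.

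Dropped in group 3 = rate × 90 × early-only share × misattributed share, rounded down. Differences are group 4 minus group 3, in percentage points, with Newcombe 95% intervals.

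| Rate | Early-only share | Dropped | Group 4 vs group 3 | Difference (95% CI) |
|---|---|---|---|---|
| 10% | 50% | 0.10 × 90 × 0.5 × 0.5 = 2.25 → 2 | 9 vs 7 | 2.2 (-6.5 to 11.1) |
| 10% | 100% | 0.10 × 90 × 1.0 × 0.5 = 4.5 → 4 | 9 vs 5 | 4.4 (-3.8 to 13.0) |
| 20% | 50% | 0.20 × 90 × 0.5 × 0.5 = 4.5 → 4 | 18 vs 14 | 4.4 (-6.8 to 15.6) |
| 20% | 100% | 0.20 × 90 × 1.0 × 0.5 = 9 | 18 vs 9 | 10.0 (-0.5 to 20.5) |

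With no misattribution the difference is zero: 9 vs 9 (-9.2 to 9.2), or 18 vs 18 (-11.7 to 11.7).

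**Illustration of omission, with perfect attribution**

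Suppose prep truly adds 10 points after dosing to a 20% rate, all of it mild to moderate, in subjects with no other recorded diarrhea. The true counts are 27 in group 3 and 18 in group 4, so group 3 minus group 4 is 10.0 points (-2.7 to 22.3). The table would show 18 vs 18, a difference of 0.0 (-11.7 to 11.7).

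**What shrinks these figures**

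- Prep is taken around 6 pm the evening before (8.1), so the share of its effect lasting past dosing may be small.
- The follow-up calls solicit "diarrhea (passage of ≥ 3 watery stools per 24-hour period for two consecutive days") in every group, which filters brief episodes. The Day 2 call asks about any AE without that definition.
- The baseline rules in 9.1.1, 9.4 and 9.5 remove symptoms already present, in every group.
- Section 10.2.5 counts subjects with at least one occurrence, so a subject with later recorded diarrhea still counts.

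**The case against.** The strongest reply is that the endpoint is the safety of the product. The synopsis and section 2 speak of the safety of the lyophilized capsules, and 9.1.1 ties an AE to use of PRIM-DJ2727. On that reading, leaving out known laxative and loperamide effects is consistent with the question asked. This stands against the omission point. It does not answer misattribution, and 10.2.3, which frames the comparison as with and without prep and Imodium, leaves the broader reading open.

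A second reply is that the information is not all lost. Follow-up diaries, handed out on Day 1, record daily bowel movements in all groups, so groups 3 and 4 could be compared without any judgment of cause. This stands in part. No analysis of those counts is planned, the diary's first day is not stated, and missed diaries are not deviations.

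Third, staff knowledge of group 4 comes with a declared open arm and is not a separate fault. That is fair, and a change of recording rule would not remove open-label reporting. It would remove the need to judge cause before an event is recorded.

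A reader might infer that the plan builds in a false significant safety advantage for group 3, or that all its early diarrhea disappears. The documents support neither. No between-group safety test is stated, only counts, percentages and listings, and the exclusion applies only to events attributed to prep or Imodium.

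**Conclusion.** The concern holds as a limited problem of unequal recording in a primary but descriptive comparison. The direction is certain from the text: only group 3's early low-grade diarrhea and constipation counts can be lowered relative to group 4's. The size is unknown and probably small. The differences of 2.2 to 10.0 points rest wholly on assumed rates, early-only shares and misattribution. The largest requires every event to be early-only and half to be misattributed, and all the intervals include zero.

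It would be wrong to extend this to the rest of the trial. Efficacy, serious AEs, halting, severe diarrhea, and moderate or later constipation are unaffected. So is the dose comparison, because groups 1-3 share the rule and are blinded to dose. The plan should still be changed: the comparison is primary, the correction is cheap, and AEs left unrecorded cannot be reliably restored at analysis.

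**What to change.** In 9.5, replace the group-specific exception with one recording rule for all four groups. Record diarrhea and constipation from Day 1 dosing through the Day 1(+3) contact, with onset and severity and a flag for events expected with prep or Imodium. Set the flag by symptom, grade and onset window, not by judged cause, so that it can also be set in group 4. The window should state whether the one-day limit applies to diarrhea.

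In 10.2.5, tabulate group 3 versus group 4 with and without flagged events, which serves both readings of the endpoint. Add a group 3 versus 4 summary of the diary bowel-movement counts already collected, with the number of diaries missing per group.

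Cost: one amended paragraph, a short addition to 10.2.5, one case report form flag, one or two extra tables, and more mild events to log. No clinical procedure changes.

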9.6 Recording and Documenting Adverse Event

The study team must completely and promptly record each new adverse event and serious adverse event that occurs after the procedure, even if the relationship of adverse event to the procedure is assessed by the Investigator to be “unlikely” or “not related”. In addition, the investigator must document and follow serious adverse events and adverse events of special interest that occur from the procedure through 180-200 days after the FMT. The Investigator should attempt, if possible, to establish a diagnosis based on the presenting signs and symptoms. If an adverse event meets the definition of a serious, unexpected and suspected (related to study drug/procedure) adverse reaction (SUSAR) then the Investigator must also complete the serious adverse event form/IND safety report, and send any supporting source documents to the University of

Texas Health Science Center IRB and FDA as soon as the event is discovered within the defined timeline.

At each visit, after the subject has had an opportunity to mention any problems spontaneously, the Investigator (or designee) will inquire about adverse event by asking the standard questions listed, such as:

- Have you had any new medical problems since your last visit?
- Have any medical problems present at your last visit changed, i.e., stopped, worsened, or improved?
- Have you taken any new medicines, other than study drug, since your last visit?

Any spontaneous adverse event information provided by the subject will be recorded. If an adverse event has not resolved at the time of the final visit, the Investigator should evaluate the status of the adverse event at the follow-up phone contact and reflect the status of the adverse event (e.g. ongoing or resolved).

The DSMB will issue a final report identifying adverse events related to study drug.

9.7 Investigator Reporting of Suspected Unexpected Serious Adverse event (SUSAR)

Adverse events that meet all three definitions described above of a Suspected (related or possibly related to study drug or participation in the research), Unexpected and Serious Adverse Reaction (SUSAR) must be reported to the University of Texas Health Science IRB and FDA expeditiously. The investigator must report an adverse event as a suspected adverse reaction only if there is evidence to suggest a causal relationship between the drug and the adverse event.

The investigator must report all suspected unexpected serious adverse reaction events to the University of Texas Health Science IRB/CPHS via iRIS within 7 calendar days after investigator recognizes or classifies the event as SUSAR unless the report involves the death of a participant, in which case the event needs to be reported to IRB within 24 hours after first knowledge by the investigator via facsimile or email or by telephone.

The investigator must also report all suspected unexpected serious adverse reactions to the FDA as soon as possible but within a maximum of 15 calendar days of first knowledge by the investigator, unless the event is *unexpected fatal or life-threatening suspected adverse reaction*, in which case the event needs to be reported to the FDA as soon as possible but in no case later than 7 calendar days after the investigator's initial receipt of the information.

The reports should identify the subject by their unique subject number instead of names. The completed serious adverse event report forms will be used by the investigators in regulatory filings. The investigator is responsible for continuing to report to the University of Texas Health Science IRB and FDA within 15 calendar days of any new or relevant follow-up information obtained concerning the SUSAR event. The results of any additional assessments conducted must also be reported to the University of Texas Health Science IRB and FDA.

Serious and unexpected adverse events can be anticipated to occur during the course of the study regardless of drug exposure. Examples of such anticipated events may include but not limited to known consequences of any underlying disease or RCDI, events anticipated from any background regimen, events common in study population or recurrence or worsening of a condition relative to pretreatment baseline. Such events will not be reported individually as they are not informative as single cases to conclude that the event is a suspected adverse reaction.

If an investigator is unsure about whether to report a finding as an adverse event, he will record the finding as an AE in study data. All adverse events will be reported in the annual and final clinical study reports as required by the applicable regulations.

